9.3 Adverse Event Reporting

9.3.1 Sponsor Reporting Requirements

Sponsor will report all SAEs to local competent authority per local requirement.

9.3.2 Clinical Site Reporting Requirements

- All AEs and ADEs will be recorded by the investigator or designee on the eCRFs provided
- Any SAEs are to be reported to the sponsor within 36 hours except UADE or suspected UADE which is to be reported within 24 hours of knowledge of the event, followed by a written confirmation by the investigator within 5 working days
- The investigator at each site is ultimately responsible for reporting AEs, SAEs and UADEs to the EC according to local EC requirements

10 MEDICAL SAFETY MONITORING

Device-related SAEs and hypoglycemic events will be reviewed and adjudicated by an independent medical monitor who has relevant expertise and is not affiliated with the sponsor or the study site. The medical monitor may require additional explanatory or supportive documents, which may include source documents from the hospital, as needed, when reviewing the events. The medical monitor will also monitor the overall safety of the study and recommending appropriate actions to the sponsor, when necessary.

11 STATISTICAL DESIGN AND ANALYSIS

11.1 Statistical Overview

The primary endpoint defined as the proportion of participants experiencing one or more device- or procedure-related serious adverse events, will be evaluated at week 12. Secondary endpoints will be assessed at time points specified in Section 3, including presentation of changes from baseline by visits for glycemic parameter, liver enzyme and other cardiometabolic metrics..

11.2 Sample Size Considerations

A minimum of 20 but up to 30 participants are planned for this study. A sample size of 20 is considered to be sufficient for the feasibility nature of this investigation.

11.3 Analysis Populations

The following analysis populations are defined for the study: Intent-to-Treat (ITT), modified Intent-to-Treat (mITT), Per-Protocol (PP) and Completed Cases (CC). The primary safety analysis will be performed on the ITT population. The primary effectiveness analysis will be performed on mITT population.

- Intent-to-Treat: The Intent-to-Treat population includes all enrolled participants as defined in Section 5.3 regardless of whether or not the participant received the full treatment.
- Modified Intent-to-Treat: The mITT population consists of the ITT population participants who received the target treatment (at least 6 cm of duodenum treatment) and that have at least one post-treatment follow-up.
- Per-Protocol: The Per-Protocol population is a subset of the mITT population and includes all participants who received the target treatment, do not have any major eligibility violations, and maintained stable glucose-lowering medications for 24 weeks post procedure.

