6.1.1.3. Allowed pre-mixed insulin includes

- NovoMix® 30 (30% rapid, 70% intermediate Protaphane)
- Humalog® Mix 25 (25% rapid, 75% intermediate Humulin NPH)
- Ryzodeg 70:30 (70% long acting Degludec, 30% rapid Aspart)
- Mixtard® 30/70 (30% short, 70% intermediate Protaphane)
- Humulin® 30/70 (30% short, 70% intermediate Humulin NPH).

For the index procedure, participants will be instructed to fast overnight. A general recommendation is to administer 50% of their typical insulin dose at their usual time typically the preceding evening or the morning of the procedure day. However, the investigator should individualize insulin management for each subject particularly if S/RA is a component of their insulin regime.

- Following the procedure, participant's baseline insulin dose will be reduced to avoid hypoglycemia in the setting of a reduced caloric intake post procedure. Subsequently the insulin dose will be titrated to achieve a fasting glucose target of 5.0 – 7.2 mmol/L. Specifically, the following algorithm will be instituted.
- Continue insulin at 50% of the baseline dose on day 1 post procedure.
- Increase insulin dose by 2 units or 10% (as per recommendation of the treating investigator or provider) if fasting glucose is above the target of 7.2 mmol/L over 3 consecutive days.
- Alternatively, reduce insulin dose by 2 units or 10% (as per recommendation of the treating investigator or provider) for a single morning blood glucose or CGM reading less 5.0 mmol/>, or any episode of symptomatic hypoglycemia.
- If daily insulin dose is reduced to 10 units or 0.1 units/kg and fasting glucose is within the target range, insulin may be discontinued with close follow up of glycemia through CGM.
- If insulin is not completely withdrawn by 24 weeks, the background therapy may be intensified to further decrease or eliminate reliance on exogenous insulin. Intensification of background therapy may include addition of a GLP-1a, or an SGLT2i if the participant is already taking or has demonstrated an intolerance to GLP-1a. The insulin titration following intensification of background glycemic therapy should follow the same algorithm as described above.

The above algorithm is provided as a guideline. Investigator should apply clinical judgement to individualize therapy including insulin dosing and background glycemic medications.

Participants in the IS cohort should be instructed to use CGM to monitor his/her glucose levels throughout the duration of the study.

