11. STATISTICAL DESIGN AND ANALYSIS

Statistical analysis will be performed in accordance with the main protocol. The data on safety and procedural feasibility will be analyzed for each cohort and overall. The data on efficacy endpoints will be analyzed by treatment cohort.

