6. ANALYSIS POPULATIONS

Patients will be considered enrolled in the study once the patient has passed endoscopic screening. Screen failures are defined as patient who consented to participate in the clinical study and started the screening tests specified by the protocol but are not subsequently enrolled in the study.

The primary and secondary safety analyses will be performed using the ITT. The primary effectiveness analyses will be performed using the FAS population. The Per-Protocol population and Completed-Cases population will be used for the sensitivity analyses of the primary and secondary effectiveness endpoints.

Intent-to-Treat: The Intent-to-Treat population includes all enrolled patients, regardless of the patient having received the target treatment (at least 6cm of duodenum treated). The point of enrollment occurs when a patient has provided written informed consent and an energy delivery has been attempted during the index procedure.

Full Analysis Set: The FAS population consists of the ITT population patients who received the target treatment (at least 6 cm of duodenum treatment) and that have at least one post-treatment follow-up examination.

Per-Protocol: The Per-Protocol population is a subset of the FAS population and includes all patients who received the target treatment, do not have any major eligibility violations, and maintained stable glucose-lowering medications for 24 weeks post-procedure. The definition of what constitutes a major eligibility violations will be established before the study database is locked.

Completed Cases: The Completed Cases population is a subset of the Per-Protocol population and includes all patients who received the target treatment, do not have any major eligibility violations, and maintained stable glucose-lowering medications for 24 weeks post-procedure, and completed the final Week 48 End of Study Visit.

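### The Per-Protocol stability criterion was written for the non-insulin cohort; applied unchanged to the insulin cohort, it leaves a set that is either empty or selected on the insulin outcome

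*Protocol*

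**What the plan says.** Protocol Section 11.3 defines PP as a subset of mITT: target treatment received, no major eligibility violation, and participants who "maintained stable glucose-lowering medications for 24 weeks post procedure". Insulin is not exempted, no cohort is distinguished, and stability after the procedure is not defined.

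Appendix 4 Section 11 gives the IS cohort no analysis sets of its own: "Statistical analysis will be performed in accordance with the main protocol". It adds: "The data on efficacy endpoints will be analyzed by treatment cohort". A separate IS PP set therefore arises.

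Appendix 4 lists insulin under glucose-lowering medications (Section 6.1) and plans for it to change. The algorithm under Section 6.1.1.3 says: "Continue insulin at 50% of the baseline dose on day 1 post procedure". It continues: "Subsequently the insulin dose will be titrated to achieve a fasting glucose target of 5.0 – 7.2 mmol/L". At a low enough dose with fasting glucose in range, "insulin may be discontinued with close follow up of glycemia through CGM". Appendix 4 Section 4 likewise states that the insulin dose will be titrated and may be discontinued. The algorithm is qualified: "The above algorithm is provided as a guideline", and investigators may individualize dosing.

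Only the non-insulin drugs are to be held stable during follow-up (Appendix 4 Section 6.1.2.3).

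On the role of PP, Protocol Section 11.3 bases the primary safety analysis on ITT and the primary effectiveness analysis on mITT. Section 11.4.3 adds PP for secondary endpoints only where judged appropriate.

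**The concern.** The stability condition makes sense for the non-insulin (NIS) cohort. There the background drugs are meant to stay fixed to Week 24, so a change in HbA1c can be read without a concurrent drug change. In the IS cohort the insulin dose is itself expected to respond to treatment. Appendix 4 Section 1 presents stopping insulin as the attractive goal, and Section 3 assesses efficacy through glycemic control without exogenous insulin. A criterion that demands stable insulin then works against the plan for that cohort. A participant who benefits as hoped fails it.

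At stake is the meaning of any IS PP result. Either no such result can be produced, or it describes a subgroup chosen by what happened to insulin after treatment.

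**Working it through.** The documents give no PP size and no power calculation, so there is no planned figure to reproduce. The check applies the PP rule to the Appendix 4 insulin algorithm.

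**Inputs**
- IS cohort size: 20 initially, up to 30 (Appendix 4 Section 4).
- Day 1 dose: 50% of the baseline dose D (Appendix 4 Section 6.1.1.3).
- Increases: 2 units or 10%, after 3 consecutive days with fasting glucose above target (same section).
- Maximum baseline dose: 60 IU/day (Appendix 4 Section 6.1.1).
- Only numeric meaning of stable insulin: at most 10% change, stated for the 3 weeks before baseline (same section). Using it after the procedure is an assumption.
- Off-insulin rate: 69% at 6 months in 16 patients treated with thermal balloon ablation (Appendix 4 Section 1). Illustration only.

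**Step 1: the day 1 change.** (D − 0.5D)/D = 50%, which is 50/10 = 5 times the 10% tolerance.

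**Step 2: shortest return to within 10% of baseline.** With k increases, at most one per 3 days, the minimum time is 3k days.
- Steps of 10% of baseline: 0.5 + 0.1k ≥ 0.9 gives k = 4, or 12 days.
- Steps of 10% of the current dose: 0.5 × 1.1^k ≥ 0.9 needs 1.1^k ≥ 1.8. Since 1.1^6 = 1.77 and 1.1^7 = 1.95, k = 7, or 21 days.
- Steps of 2 units: 0.5D + 2k ≥ 0.9D gives k ≥ 0.2D. For D = 10, 20, 40 and 60 IU, k = 2, 4, 8 and 12, or 6, 12, 24 and 36 days.

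So a participant who follows the algorithm is outside the tolerance for at least 6 to 36 days of the 24 × 7 = 168 days, even if every fasting reading calls for an increase.

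**Step 3: the IS PP set under three readings**

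| Reading of stable | Who can be in PP | Size |
|---|---|---|
| A. Insulin counts; clock starts at the procedure; algorithm followed | Nobody | 0 of 20 to 30 |
| B. Insulin counts; early re-titration tolerated | Those whose insulin returns to about baseline and stays there | Not fixed by the documents |
| C. Insulin exempt; non-insulin drugs must be stable | Anyone who meets the other PP conditions | Up to 20 to 30 |

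**Step 4: scale of reading B.** If 69% stopped insulin, 20 × (1 − 0.69) = 6.2 and 30 × (1 − 0.69) = 9.3 would remain. These are upper limits, because participants who reduce insulin without stopping are dropped as well.

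**Step 5: what reading B does to the estimate.** No one who is off insulin at Week 24 can be in the set. A PP proportion of participants free of insulin at 24 weeks would therefore be 0 by construction, whatever the device does. The IS endpoint row in Appendix 4 Table 1 is only partly legible in the text available, but what remains concerns insulin at 24 weeks, maintained at 48 weeks. For HbA1c, the documents do not settle the direction of the distortion.

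**The case against.** The strongest counter-argument is that the set is not shown to be empty. The algorithm is a guideline, stability has no post-procedure definition, and Section 11.4.3 already allows PP to be left out. This stands in part. A reader might infer that the IS PP set is empty by rule, or that anyone in it ignored the titration plan. The documents support neither. A participant whose fasting glucose drives the dose back to about baseline has followed the plan and could qualify under reading B. Individualized dosing is also allowed. The discretion over when to use PP does not correct the criterion, though. It leaves the choice open, and the SAP's commitment to settle definitions before lock covers major eligibility violations (Section 6), not drug stability.

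Two wider inferences should also be resisted.
- **Completed Cases.** The SAP says "The Completed Cases population is a subset of the Per-Protocol population", so a reader might conclude that this set fails for the IS cohort too. But Protocol Section 11.3 names Completed Cases without defining it. The nesting comes from a SAP titled for REGENT-1-US (Doc. No. 346) that tabulates 20 patients from a non-insulin population. Its only references to an IS population are format notes for adverse event tables. Neither document plans a Completed Cases analysis for the IS cohort.
- **The NIS cohort.** A reader might say that the peri-procedural cuts and holds in Section 6.2.2.1 break the condition there as well. Section 6.2.1 gives the intended reading: drugs return to the background level during the transitional diet and are then held to Week 24. The sulfonylurea share in the cited hydrothermal study is no measure of any NIS loss. It describes another device's patients, and a literal reading would also count metformin and SGLT2i holds.

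**Conclusion.** The point holds in conditional form. The IS PP set has no workable definition: it is empty under reading A and selected on the intended outcome under reading B. Only reading C gives a usable set, and the text does not state it.

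The figure of 0 of 20 to 30 assumes that insulin counts as a glucose-lowering medication, that stability is judged against the baseline dose from the procedure onward, and that the guideline is followed. If stability were judged only against the day 1 dose, a participant left at half dose throughout would pass. Main protocol Section 6.2.1 ties stability to the background level, however, and anyone titrated or taken off insulin would still fail. The 6 of 20 and 9 of 30 rest on an outside rate and show scale only.

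The consequence is limited. PP is supplementary, the secondary endpoint summaries are descriptive, and no primary IS result depends on it. The correction is worth making because it is cheap and because the present rule would remove the participants in whom the treatment did what was hoped.

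**What to change.** Amend Protocol Section 11.3 and Appendix 4 Section 11 before database lock, in one of two ways:

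1. For the IS cohort, apply the stability criterion to non-insulin glucose-lowering drugs only, from the end of the peri-procedural period to Week 24. State that insulin changes made under Appendix 4, including the individualization it permits, are not PP violations.
2. State that PP is not used for the IS cohort.

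The second is simpler. The first keeps a sensitivity analysis, and because it accepts individualized dosing it does not turn a guideline into an inclusion test. Either costs a sentence or two in each place. Neither changes clinical management or data collection, since medication changes and their reasons are already recorded on the eCRF.

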11.4 Statistical Analysis

11.4.1 Accountability and Demographics

The number of participants completing the study and withdrawing from the study will be presented along with reasons for withdrawal.

Descriptive summaries for baseline medical history and demographic characteristics including age, gender, height, weight, baseline BMI, diabetes history, glycemic parameters, and baseline medications will be presented.

11.4.2 Primary Endpoint Analysis

The primary endpoint of the study is proportion of participants experiencing one or more device- or procedure-related serious adverse events within 12 weeks post procedure. The analysis will be performed using the ITT population. No hypothesis will be tested as the analytical intent is to characterize outcomes.

Additionally, an overall summary of AEs will be provided including the number of events and percent of participants with any AEs, SAEs, and UADEs. For each type of event, the number of events and number and percent of participants with the event will be provided. Separate summaries of all adverse events will be summarized by relationship to device and procedure.

Only events occurred at or after the index procedure will be counted for the purpose of safety analysis. Events occurred prior to the index procedure will be considered as medical history.

11.4.3 Secondary Endpoint Analysis

Secondary endpoints are summarized in Section 3. The primary analysis of the study's secondary endpoints will be performed using the mITT population. The analysis will also be performed using the PP population when appropriate.

Results will be summarized by mean, standard deviation, median, minimum and maximum of continuous variables; and by number and frequency (with percentages) of categorical variables.

12 QUALITY CONTROL AND QUALITY ASSURANCE

12.1 Selection of Study Sites and Investigators

The sponsor will select investigators who are qualified by training and experience to perform clinical research in this field and to participate in the clinical investigation. Sites will be selected based upon an assessment of the qualifications of the Primary Investigator and the facilities at each site. All investigators will be trained on the device, the protocol and all study procedures prior to enrolling participants.

A pre-investigation visit will be conducted at each study site to assure that the investigator and the study staff understand the obligations for using and managing the investigational device, following the study protocol, obtaining informed consent, adhering to GCP and local regulations, and conducting clinical research.

12.2 Training

12.2.1 Site Training

All investigators/study personnel are required to attend sponsor training sessions, which may be conducted at a site initiation visit or other appropriate training sessions. Remote over-the-phone or web-based training will take place as necessary. Training of investigators/study personnel will include, but is not limited to, the investigational plan, participant recruitment, enrollment (including review of inclusion and exclusion criteria), participant retention, investigational device usage, protocol requirements, case report form completion, and study personnel responsibilities. At least one individual at each site also will be trained on the delivery of the lifestyle modification counseling for diabetes and diabetes patient education. All investigators/study personnel that are trained must sign a training log (or an equivalent) upon completion of the training. Investigator/study personnel must not perform any study-related procedures prior to being trained.

Investigators who perform the Endogenex procedure will be trained on device use. Sponsor personnel will provide technical support for all the Endogenex procedures during the study.

12.2.2 Monitor Training

The sponsor or designee will engage monitors that are qualified by appropriate training and experience to review the conduct and quality of the study. Prior to working on the study, monitors will be trained to the investigational plan, case report forms, and the device/procedure knowledge. Such training will be documented.

12.2.3 Study Monitoring

Sponsor and/or a designee (e.g., a Contract Research Organization), will monitor the clinical study in a manner consistent with local regulations and the Good Clinical Practice (GCP) standards adopted by the sponsor.

The investigator is required to ensure compliance with all procedures required by the Investigational plan and by study procedures provided by the sponsor. The investigator agrees to provide reliable data and all information requested by the Investigational Plan including eCRFs, discrepancy clarification requests or other appropriate instruments according to the instructions provided, and to ensure direct access to source documents by sponsor representatives.

Clinical Monitors will periodically monitor all eCRFs and corresponding source medical records for each participant. The monitoring visits provide the sponsor with the opportunity to evaluate the progress of the study, to verify the accuracy and completeness of eCRFs, to resolve any inconsistencies in the study records, and to ensure that all protocol requirements, applicable regulatory regulations, and investigator's obligations are being fulfilled. Monitoring and data verification may be performed remotely or onsite.

The investigator and his/her staff will be expected to cooperate with sponsor's personnel or designee and to be available during the monitoring visits to answer questions sufficiently and to provide any missing information. Monitoring visits may be performed remotely, especially in consideration of COVID-19. The Investigator and his/her staff will provide necessary assistance to facilitate remote monitoring.

12.3 Source Data Verification

Source data verification ensures accuracy and credibility of the data obtained. During monitoring, reported data is reviewed with regard to being accurate, complete, and verifiable from source documents (e.g., participant files, physician notes, discharge summaries, operative records, study worksheets, etc.). All data reported on the eCRF should be supported by source documents, unless the eCRF also serves as a source document. Source data verification may be performed remotely.

12.3.1 Definition of Source Data

Source data includes all information in source documents (original records, certified copies of original records, appointment books, original laboratory records, CGM data, and original data recorded on customized worksheets) and includes all original recordings or copies of clinical findings, observations, or other activities in a clinical study necessary for the reconstruction and evaluation of the study. Certain data may be directly entered into eCRF. In this case, the eCRF serves as source document.

12.3.2 Direct Access to Source Data/Documents

The investigator(s)/institution(s) will permit direct access to source data/documents for study-related monitoring, audits, EC and regulatory inspection(s). For remote source data verification, the Investigator and his/her staff will provide the study monitor remote access to source records.

Consenting participants are agreeing to allow the sponsor or designee access and copying rights to pertinent information in their medical records and their CGM data relevant to study participation. As part of the informed consent, the investigator or designee will obtain permission for regulatory authorities to review any records identifying participants in this study. The sponsor will not otherwise release any personal information (refer to **Section 14.3 Confidentiality**).

